## **V. Primary Outcome Analysis**

The primary endpoint of the study is whether or not the subject is alive and capable of walking 10 feet or across a room without human assistance at 60 days post-randomization. As per the study protocol, the day 60 assessment will be performed within a window of 31-90 days post-randomization, although every effort will be made to make the assessment as close to day 60 as

possible. Results of assessments performed outside the 31-90 day window will be considered as missing data. The treatment effect will be evaluated using the Mantel-Haenszel (MH) test for difference in proportions, stratified by sex, fracture type, and country. The MH relative risk (RR) of spinal anesthesia (SA) vs. general anesthesia (GA) will be reported. *The Breslow-Day test* (Breslow and Day, 1980) will be used to test homogeneity of the RRs across strata. If there is statistically significant heterogeneity, we will report separate RRs within strata.

The walking ability component of the primary outcome will be assessed by a telephone interview with the subject conducted as close to day 60 as possible; information obtained during a 31-90-day window after randomization will be considered acceptable for analysis. To assess walking ability, respondents were asked to indicate whether on average in the 7 days prior to the interview they used/received human assistance to ambulate. Individuals indicating that they did not ambulate at all over the 7 days preceding the interview were coded as having met the study outcome. Vital status will be assessed at the day 60 telephone interview; for patients who cannot be reached for the 60-day telephone interview, vital status at 60 days will be assessed via telephone follow up at subsequent time points. Additional information on deaths prior to day 60 will be obtained from site Adverse Event reports and via a National Death Index search for patients who were randomized at US sites and for whom sufficient identifying information is available. Patients who are known to have died by day 60 will be assessed as having met the primary outcome, regardless of walking status assessments prior to that point. Those known to be alive at day 60 but without a response to the question about capability of walking 10 feet will be considered to be missing the primary outcome. In cases where patients were unable to provide their own responses to the primary outcome assessment (e.g., due to dementia or acute illness), data were collected from alternate (proxy) respondents as described in the main study protocol. Subjects for whom information on both components of the primary endpoint are missing (i.e., patient has become lost to follow-up so that neither survival status nor walking ability is known) will be excluded from the primary analysis, but a variety of sensitivity analyses, described below, will be conducted to assess the potential influence of these exclusions on the comparison of outcomes.

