## VI. Secondary Outcome Analyses

VI.1. 60 day mortality. This component of the primary endpoint will be assessed via site reports of deaths and at the day 60 telephone interview, and will be analyzed as a binary outcome using the MH method, stratified by sex, fracture type, and country. Patients who are unable to be assessed directly or by proxy at the 60-day telephone interview but who are known to be alive at later time points will be categorized as alive at day 60. Additional information on deaths prior to day 60 will be obtained via a National Death Index search for patients who were randomized at US sites with sufficient identifying information and for whom no follow-up at or beyond day 60 is available. The Breslow-Day test will be used to assess homogeneity of the RRs across strata.

VI.2. Ability to walk 10 feet without human assistance at 60 days post-randomization. This component of the primary endpoint will be analyzed as a binary outcome, using the MH test stratified by sex, fracture type, and country. Participants who died prior to completing the 60 day interview or had no informative answer to the ambulation assessment will be excluded from the analysis.

VI.3. New-onset delirium. This outcome will be determined by baseline and post-operative 3D CAM tests. Subjects will have a baseline 3D-CAM assessment prior to randomization and assessments on days 1, 2 and 3 post-surgery, with fewer assessments if discharged, withdrawn, or died prior to day 3. Only subjects with a baseline 3D-CAM assessment but no delirium will be included in the analysis. Subjects with a positive response on any post-surgery assessment will be classified as positive for new onset delirium. Subjects who had 1 or more post-surgery assessments with none positive for delirium will be classified as negative for this outcome. Subjects without any post-surgery 3D-CAM response will be excluded from this analysis. This binary outcome will be analyzed using the MH method, stratified by sex, fracture type, and country. The Breslow-Day test will be used to assess homogeneity of the RRs across strata.

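### Does the SAP contradict itself on which state is the primary outcome event?

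*SAP*

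**What the plan says.** SAP section V (Primary Outcome Analysis) introduces the endpoint with "The primary endpoint of the study is whether or not the subject is alive and capable of walking 10 feet" and goes on to require that the walking be done without another person's help at day 60.

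Later in the same section come two coding rules. For deaths: "Patients who are known to have died by day 60 will be assessed as having met the primary outcome". For people who were not walking: "Individuals indicating that they did not ambulate at all over the 7 days preceding the interview were coded as having met the study outcome". The interview item asks "whether on average in the 7 days prior to the interview they used/received human assistance to ambulate"; the text does not add which answer counts as the event.

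On analysis, section V states "The treatment effect will be evaluated using the Mantel-Haenszel (MH) test for difference in proportions, stratified by sex, fracture type, and country", then "The MH relative risk (RR) of spinal anesthesia (SA) vs. general anesthesia (GA) will be reported". Homogeneity across strata is checked with the Breslow-Day test, and "If there is statistically significant heterogeneity, we will report separate RRs within strata".

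Section VI takes the two components separately. VI.1 is 60-day mortality. VI.2 is headed "Ability to walk 10 feet without human assistance at 60 days post-randomization", is analysed as a binary outcome with the MH test, and excludes participants who died before the interview.

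**The concern.** Read quickly, section V has a dead patient meeting an endpoint that consists of being alive and walking. Only the favourable state is spelled out in the definition, while the coding rules use *met* for the unfavourable one. No single sentence joins the two or names the event for the relative risk.

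That would matter because a relative risk, unlike an odds ratio, does not simply invert when event and non-event are swapped. If analysts could legitimately choose either direction, the size of the headline estimate and the pattern of stratum-specific relative risks would rest on a choice left open until after unblinding. The components add to the impression: mortality in VI.1 is named as a failure and walking in VI.2 as a success. On the most literal reading, deaths and non-walkers would be pooled with independent walkers, and the endpoint would mean nothing.

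**Working it through.** **Step 1: do the passages yield one event?**

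- The definition says *whether or not*. That describes a variable with two values and does not say which one is counted.
- The coding rule for deaths puts death on the side that has met the outcome.
- The coding rule for people who did not walk puts them on the same side.
- Someone who walks only with another person's help is not in the favourable state of the definition. The variable has two values and the other one is already labelled as the event, so this person falls on the event side too.
- Other sections agree. V.2 speaks of the risk of the primary outcome among compliers. VI.1 calls mortality a component of the primary endpoint. VII.4b groups death with inability to walk as worsening.

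The one coding consistent with all of this is: event = dead by day 60, or alive but unable to walk the stated distance unaided.

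**Step 2: how much would reversal matter if the direction were open?** The SAP gives no event rates, so every risk below is an assumption. With comparator failure risk q and failure relative risk RR:

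success RR = (1 − q × RR) / (1 − q)

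| q | failure RR | success RR |
|---|---|---|
| 0.10 | 0.80 | 0.92 / 0.90 = 1.022 |
| 0.18 | 0.80 | 0.856 / 0.82 = 1.044 |
| 0.20 | 0.80 | 0.84 / 0.80 = 1.050 |
| 0.30 | 0.80 | 0.76 / 0.70 = 1.086 |
| 0.40 | 0.80 | 0.68 / 0.60 = 1.133 |

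The asymmetry is real.

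**Step 3: what happens to the planned analysis?** Take two strata with 500 per arm in each, and failure risks (spinal vs general) of 15% vs 20% and 30% vs 40%. Failures are 75 vs 100 and 150 vs 200.

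MH RR = Σ(x₁n₀/N) / Σ(x₀n₁/N)

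- Failure as event: (37.5 + 75) / (50 + 100) = 112.5 / 150 = 0.750.
- Success as event: (212.5 + 175) / (200 + 150) = 387.5 / 350 = 1.107, whose reciprocal is 0.903.

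MH test: z = (Σx₁ − ΣE) / √ΣV, with E = n₁m/N and V = n₁n₀m(N − m) / [N²(N − 1)], where m is the total number of events in the stratum.

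- Failure: Σx₁ = 225 and ΣE = 87.5 + 175 = 262.5. ΣV = 36.13 + 56.93 = 93.06. So z = −37.5 / 9.647 = −3.887, p = 0.0001.
- Success: m and N − m change places, so V is the same and only the sign of the numerator changes. z = +3.887, p = 0.0001.

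Two other assumed sets of risks behave the same way:

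| Failure risks (spinal/general), two strata | MH RR, failure | MH RR, success | p, either coding |
|---|---|---|---|
| 10%/12% and 20%/24% | 0.833 | 1.037 | 0.068 |
| 30%/36% and 40%/48% | 0.833 | 1.121 | 0.0012 |

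**Step 4: weighting.** The MH RR is a ratio of standardised risks with stratum weights n₁n₀/N, which contain no event counts. In the worked example the standardised failure risks are 22.5% and 30%. The success RR is (1 − 0.225) / (1 − 0.30) = 1.107, as above. Either relative risk can be obtained from the same two risks.

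**Step 5: homogeneity.** Stratum relative risks of 0.75 and 0.75 for failure become 1.062 and 1.167 for success. The Breslow-Day test as normally defined compares odds ratios, and these only invert. For failure they are (0.15/0.85)/(0.20/0.80) = 0.706 and (0.30/0.70)/(0.40/0.60) = 0.643. For success they are 1.417 and 1.556. The ratio between strata is 1.098 either way, so the test result, and with it the trigger for reporting by stratum, does not depend on the labelling.

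**The case for a change.** The strongest reply is that a neutral binary still needs a named event once a relative risk is reported, and that section V names only the favourable state where the endpoint is defined. The reader has to take the direction from two coding remarks, and the group that walks only with help is placed by inference. The sensitivity analyses in V.1 and V.2 carry the same unnamed event. An SAP exists to settle such things before unblinding, and settling this one would take a few sentences.

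As a comment on drafting, this stands: section V would be clearer with the event stated in one place. The reply does not show that two codings are open. Both remarks point the same way, and nothing in the SAP labels the favourable state as the event. Pooling deaths with independent walkers is not something an analyst would program.

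VI.2 carries less weight than its heading suggests. The text specifies a binary outcome and an MH test, with no event and no direction for a relative risk. Its two-sided test is indifferent to labelling, and a table row headed as ability to walk can be read correctly beside one for mortality.

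Section V does describe Breslow-Day as a test of relative risks, which is loose. If analysts used a genuine test of relative-risk homogeneity instead, its result would depend on the coding. That coding would still be the failure one fixed in section V.

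**Conclusion.** The concern does not call for a change. Section V describes a two-valued variable and then fixes its direction, twice and consistently, as death or inability to walk unaided. Followed as written, the plan gives a failure-direction MH relative risk, with values below 1 favouring spinal anesthesia. An explicit sentence naming the event would give the same result.

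The possible difference in the estimate (0.750 against 1.107 in the worked example, under assumed risks) would arise only if the direction were open, and it is not. The primary two-sided p-value, the MH stratum weights and the odds-ratio-based Breslow-Day result are the same under either consistent labelling. What remains is loose wording that analysts will resolve sensibly.

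This rests on two assumptions: that *whether or not* is read in its ordinary sense, and that Breslow-Day is run in its usual odds-ratio form.

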#### **VIII. Subgroup Analyses**

We will evaluate treatment difference in the subgroups defined by the following stratification variables:

- a. Sex: Male vs. Female, defined as per stratification
- b. Fracture type: Femoral neck vs intertrochanteric/subtrochanteric, defined as per stratification
- c. Country of enrollment: Canada vs US
- d. Need for assistive devices to ambulate prior to fracture: present vs. absent
- e. Age category: “oldest old” (85 years and over) vs all others
- f. History of Alzheimer’s disease or other dementia: present vs absent
- g. History of chronic obstructive pulmonary disease or asthma: present vs absent
- h. History of coronary artery disease or prior myocardial infarction: present vs absent
- i. Community residence prior to fracture: home or independent living retirement home vs nursing home, rehabilitation or acute care hospital vs other.

The first step will be to test for interaction between treatment and variable defining the subgroups. Analysis within subgroups will be performed for any variable showing an interaction yielding a p-value of 0.20 or less. Subgroup analyses will be analyzed similarly as for primary analysis.

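### The Breslow-Day test is assigned to homogeneity of relative risks but tests homogeneity of odds ratios, and for the primary outcome a reporting rule rests on it

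*SAP*

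**What the plan says.** SAP section V fixes the effect measure for the primary outcome: "The MH relative risk (RR) of spinal anesthesia (SA) vs. general anesthesia (GA) will be reported". The analysis is stratified by sex, fracture type and country. The homogeneity test and the consequence attached to it come next. The Breslow-Day test "will be used to test homogeneity of the RRs across strata. If there is statistically significant heterogeneity, we will report separate RRs within strata". The reference given for the test is a volume on case-control studies.

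Sections VI.1 (60-day mortality) and VI.3 (new-onset delirium) use nearly the same sentence: "The Breslow-Day test will be used to assess homogeneity of the RRs across strata". Neither attaches a reporting rule.

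Section V describes the endpoint in two directions. Its opening gives it as "whether or not the subject is alive and capable of walking 10 feet or across a room without human assistance at 60 days post-randomization". Further on it says "Patients who are known to have died by day 60 will be assessed as having met the primary outcome", so there the unfavourable state counts as the event.

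Section VIII has a separate screen that covers the same three factors, among others: "Analysis within subgroups will be performed for any variable showing an interaction yielding a p-value of 0.20 or less". It does not state the scale of that interaction.

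**The concern.** Breslow-Day compares the observed cell in each stratum with the cell expected under a common Mantel-Haenszel odds ratio. It therefore tests whether odds ratios are equal. If treatment has an effect and baseline risk differs between strata, equal RRs imply unequal odds ratios, and equal odds ratios imply unequal RRs. The plan thus names a test that does not address the hypothesis it states.

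In VI.1 and VI.3 this is only a mislabelled test. In V a decision depends on it. Stratum-specific RRs could be reported as evidence of heterogeneity when the RR is constant, or left out when the RRs differ but the odds ratios do not.

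**Working it through.** The SAP gives no sample size, event rate or homogeneity statistic, so there is no planned figure to reproduce. The check uses algebra and simulation.

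**Inputs from the SAP.** The measure is the RR (V). There are 2 × 2 × 2 = 8 strata from sex, fracture type and country (V). The level is 0.05, two-sided (IV).

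**Assumptions, none from the SAP.** 1600 subjects, 1:1; stratum shares from sex 67/33, fracture type 50/50 and country 80/20; control risks evenly spaced over the stated range, in ascending and descending stratum order; 20,000 runs per setting; Tarone-corrected Breslow-Day.

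**Step 1: a common RR is not a common odds ratio.** With control risk p0, OR = RR(1 − p0)/(1 − RR·p0).
- RR 0.6: at p0 = 0.10, 0.6 × 0.90/0.94 = 0.574; at p0 = 0.50, 0.6 × 0.50/0.70 = 0.429.
- RR 1.5: at p0 = 0.10, 1.5 × 0.90/0.85 = 1.588; at p0 = 0.50, 1.5 × 0.50/0.25 = 3.00.

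**Step 2: dependence on event coding.** Exchanging event and non-event inverts every odds ratio, so the Breslow-Day p-value does not change. Homogeneity of RRs does change. If the failure RR is 0.6 throughout, the success RR is (1 − 0.6·p0)/(1 − p0): 0.94/0.90 = 1.044 at p0 = 0.10 and 0.70/0.50 = 1.400 at p0 = 0.50. A test that ignores the coding cannot test a hypothesis that depends on it.

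**Step 3: rejection rates when the RR is truly common (nominal 5%).**

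| Control risks | Common RR | Breslow-Day | 7-df log-link likelihood-ratio test |
|---|---|---|---|
| 10–50% | 0.6 | 7.1–7.6% | 5.9–6.3% |
| 10–50% | 1.3 | 7.4–9.6% | 5.5–6.1% |
| 10–50% | 1.5 | 15.2–23.8% | 5.4–5.8% |
| 15–30% | 0.6 to 1.5 | 4.9–5.8% | 5.5–6.4% |

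Repeat simulations of the 10–50% rows gave 6.6–7.8%, 7.1–9.2% and 14.6–24.4% for Breslow-Day. For weaker effects at risks of 10–50%, Breslow-Day rejected 5.1–5.8% at RR 0.8, 0.9 and 1.1, and 7.0–7.4% at RR 1.25. If success is the event, with assumed success proportions of 70–85%, it rejected 6.2–6.8% at a common RR of 0.9 and 8.0–13.0% at 1.1.

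**Step 4: the reverse case.** With a common odds ratio of 0.6 and risks of 10–50%, the RRs run from 0.625 to 0.750. Over common odds ratios of 0.6, 1.3 and 1.5, Breslow-Day rejects 4.8–5.3% and the likelihood-ratio test 6.2–7.8%. Changing the test therefore gives no useful gain in detecting RR heterogeneity of this size.

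**Step 5: sparse strata (mortality).** With assumed death risks of 2–8% and a common RR of 0.6, 1.0 or 1.3, at least one stratum arm had no deaths in 64–90% of runs. Rejection rates were 3.6–4.3% for Breslow-Day, 7.9–8.6% for the 7-df likelihood-ratio test and 0.1–0.5% for an inverse-variance chi-square on log RRs. A 1-df log-link test for each factor rejected 5.1–6.0%.

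**The case against.** The best counter-argument accepts that the label is wrong and says that little follows from it.

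- **The primary inference is untouched.** Only one conditional reporting rule in V depends on the test. This stands.
- **The distortion is small for modest effects.** For failure RRs of 0.8 to 1.1, Breslow-Day rejects 5.1–5.8% even with risks of 10–50%, so the replacement is no better calibrated there. The 15–24% figure needs RR 1.5 and a fivefold spread of baseline risk. This stands for failure coding. It is weaker for success coding, where a common RR of 1.1 already gave 8.0–13.0%.
- **The event is already fixed.** Later text in V counts death and not walking as meeting the outcome. That is the natural reading, but the opening of V describes the favourable state, so a clarifying sentence is still needed.
- **Section VIII gives a second route.** It tests interaction with the same three factors at a looser threshold. It states no scale and does not cover the 8 cross-classified cells, so it does not correct V.
- **The replacement may be less robust.** A log-binomial model can fail to converge, and no simulation was done for delirium. This stands, and the fix allows for it.

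**Conclusion.** The point holds. In V, VI.1 and VI.3 the plan attributes to Breslow-Day a hypothesis that it does not test, and nothing elsewhere in the SAP corrects this. For the primary outcome a pre-specified reporting decision rests on the mismatch. For mortality and delirium it is a labelling error.

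The practical size is limited. The mismatch vanishes if there is no treatment effect or if baseline risks are equal. It is negligible at control risks of 15–30%. With failure as the event, it becomes material (15–24% rejection against a nominal 5%) only when a strong effect meets widely differing baseline risks. All rates rest on the assumed sample size, stratum shares and risks. The mismatch itself rests on none of them. It should be corrected, but it does not threaten the primary test or the pooled RR.

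**What to change.** **Section V.** State that the event is death or inability to walk without human assistance, if that is the intended coding. Replace Breslow-Day with a likelihood-ratio test of treatment-by-stratum interaction in a log-binomial model, and name a fallback in case the model does not converge. Say whether stratum-specific RRs are reported in addition to the pooled RR.

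**Section VI.3 (delirium).** Make the same replacement. If strata turn out sparse after the planned exclusions, follow the mortality approach.

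**Section VI.1 (60-day mortality).** Do not use the 7-df likelihood-ratio test or an inverse-variance chi-square on log RRs. Either test treatment interaction with sex, fracture type and country separately (1 df each, log link, stratum intercepts), or keep Breslow-Day and call it a test of odds-ratio homogeneity.

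**Minimum.** If the sponsor prefers to keep Breslow-Day throughout, correct the label in all three places and say in V that the rule is an odds-ratio screen.

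**Cost.** A few sentences and no data. The downsides are convergence handling for the log-binomial model and three tests instead of one for mortality, to be read as descriptive.

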#### **V.1. Sensitivity Analysis for Missing Data**

Baseline characteristics of patients with missing primary outcome will be compared with the baseline characteristics of those included in the analysis to assess potential for bias based on these missing values.

The primary analysis will use complete data, excluding individuals without outcome data. To assess the potential for bias incurred by ignoring the missing data, we will conduct a sensitivity analysis under the assumption of missing at random (MAR) using the inverse-probability-weighting (IPW) method (Hogan and Lancaster, 2004). In the calculation of the M-H RR and test statistic, each subject will be weighted by the inverse probability of being a complete case. We will use the non-missing rate of the primary outcome within each treatment and each stratum to estimate this probability.

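### Without a walking answer in the window, a patient enters the primary analysis only as a death, and the V.1 weights, constant within each arm and stratum, cannot detect or correct this selection

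*SAP*

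**What the plan says.** Section V defines the endpoint as "whether or not the subject is alive and capable of walking 10 feet or across a room without human assistance at 60 days post-randomization"; the event analysed is the failure, that is, death or not walking unaided. The two components are ascertained by different rules.

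- **Deaths.** "Patients who are known to have died by day 60 will be assessed as having met the primary outcome, regardless of walking status assessments" made earlier. Vital status comes from the day-60 interview and, for those not reached then, from later calls. Deaths are also sought in the sites' adverse event reports and, beyond these, "via a National Death Index search for patients who were randomized at US sites and for whom sufficient identifying information is available".
- **Walking.** The answer comes from a telephone interview with the patient, or with a proxy if the patient cannot respond. "Results of assessments performed outside the 31-90 day window will be considered as missing data".
- **Survivors without an answer.** "Those known to be alive at day 60 but without a response to the question about capability of walking 10 feet" are missing the primary outcome. Patients for whom neither component is known are excluded.

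Section V.1 makes the primary analysis a complete-case analysis. It adds an inverse-probability-weighted analysis, described as valid under missing at random, in which each complete case is weighted by the inverse probability of being complete. For that probability: "We will use the non-missing rate of the primary outcome within each treatment and each stratum to estimate this probability". Section V promises several sensitivity analyses for these exclusions. V.1 describes a baseline comparison and this weighting, and only the weighting re-estimates the treatment effect for missing outcomes.

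**The concern.** Being known to have died is enough for inclusion, whereas survival needs a walking answer as well. Among patients with no in-window answer from self or proxy, those known to have died are in and all the others are out, whether traced alive or lost. The probability of being a complete case therefore depends on vital status, which is part of the outcome.

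Vital status is observed for known deaths and traced survivors, so an analysis under missing at random could use it. A single rate per arm and stratum ignores it and in effect assumes that completeness is unrelated to vital status within a cell. The SAP's own scoring rule contradicts that, because a known death is complete by definition. At stake are the event proportions in each arm, the share of deaths in the composite and, if response differs by arm, the relative risk. The planned check would show close agreement with the primary analysis whether or not the selection mattered.

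**Working it through.** The SAP gives no event rate, missing rate or sample size, so there is no planned figure to reproduce. All rates below are assumptions.

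**Notation.** d = death risk by day 60; q = risk of not walking unaided among survivors who respond; m = share of survivors without a walking answer. Unless stated otherwise, all deaths are traced and non-responding survivors walk like responders.

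**1. Complete-case risk.**

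True risk = d + (1-d)q.
Complete-case risk = [d + (1-d)(1-m)q] / [d + (1-d)(1-m)].

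With d = 0.05 and q = 0.15, the true risk is 0.05 + 0.95 x 0.15 = 19.25%.

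| m | complete-case risk |
|---|---|
| 10% | 0.17825 / 0.905 = 19.7% |
| 20% | 0.164 / 0.81 = 20.2% |
| 30% | 0.14975 / 0.715 = 20.9% |

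For d from 3% to 10%, q from 15% to 30% and m from 5% to 20%, the excess is 0.1 to 1.9 percentage points.

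**2. What the planned weight does.** In a cell with E events among N complete cases out of n randomised, every complete case has weight n/N. The weighted risk is (E x n/N) / (N x n/N) = E/N, the unweighted risk. Only the relative weight of the strata changes. At m = 10% the weighted cell contains 0.05 / 0.905 = 5.5% deaths, against the 5% that occurred.

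An illustration with three strata of 200, 100 and 60 patients per arm (first arm vs second arm):

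| stratum | d | q | m |
|---|---|---|---|
| 1 | 5% both | 12% vs 15% | 15% vs 5% |
| 2 | 10% both | 25% both | 20% vs 5% |
| 3 | 5% both | 20% both | 5% vs 15% |

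The Mantel-Haenszel relative risk is 0.957 for complete cases, 0.958 with the planned weights, and 0.933 when only responding survivors are weighted. The true value is 0.933.

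**3. Direction.** Let non-responding survivors fail at rate r. With d = 0.05, q = 0.15 and m = 0.10:

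True risk = 0.05 + 0.95 x (0.9 x 0.15 + 0.1r) = 0.17825 + 0.095r.

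At r = 15% this is 19.25%, below the observed 19.7%. At r = 19.7% the two are equal. At r = 50% the true risk is 22.6%, above the observed value.

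**4. Untraced deaths.** If 10% of deaths also go untraced and are excluded, the complete-case risk is (0.045 + 0.855 x 0.15) / 0.9 = 19.25%, and the bias is gone.

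**5. Relative risk.** With no true effect and equal missingness it is 1.00. With no true effect, d = 5% and q = 15%:

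- 16% vs 8% missing: 0.2001 / 0.1960 = 1.02.
- 25% vs 10% missing: 0.2057 / 0.1970 = 1.04.

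Other assumed mixes at 25% vs 10% give 1.06 (d = 5%, q = 10%) and 1.07 (d = 8%, q = 12%). With a true effect and 10% missing in both arms, the shift is under 0.01 (for example 0.852 to 0.856, or 0.912 to 0.905).

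**The case against.** Counting deaths as events is inherent in the composite and is not an error. The other side can fairly add four points.

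- **The sign is unknown.** A reader might infer that the plan always overstates the event rate. The SAP says nothing about how non-responding survivors walk, and step 3 shows that the bias can vanish or reverse. This stands.
- **Deaths are not certain to be found.** The Death Index search covers only US patients with sufficient identifiers; other deaths depend on calls and site reports. This stands too. The fault is one common rate for deaths and survivors, not that no death could be missing.
- **Survivor-only weights are not always closer to the truth.** If 10% of deaths are untraced and those patients are counted as survivors, they give 0.045 + 0.955 x 0.15 = 18.8% against 19.25%, where the complete-case estimate would be right. At r = 50% they give 19.25%, further from 22.6% than the complete-case 19.7%. This stands as a reason to add a rule for unknown vital status and a range for r. It does not defend a weight that leaves every cell risk as it was.
- **The comparison moves little** unless missingness differs by arm, and the SAP gives no reason to expect a large difference. This stands.

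A reader might also infer a second error in VI.1 or VII.4.a: that the search adds deaths while searched patients without a match are dropped. VI.1 says "Additional information on deaths prior to day 60 will be obtained via a National Death Index search for patients" at US sites with sufficient identifiers and no follow-up at or beyond day 60, and does not say how a non-match is coded. The search could equally be meant to settle vital status, and the Cox model in VII.4.a may keep such patients as censored. The handling is unstated; an exclusion cannot be read into it.

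**Conclusion.** The concern holds in a limited form. The complete-case set is selected on the outcome, and the V.1 weighting cannot detect or correct this. Both follow from the SAP's rules and need no assumed rate. The size and direction do depend on assumptions. If non-responding survivors walk like responders and deaths are traced, the event rate is overstated by roughly half a percentage point at 5% mortality, 15% non-walking and 10% missing; frailer non-responders could cancel or reverse that. The relative risk is affected mainly, and modestly, when missingness differs by arm. The consequence is a missing-data check that gives unwarranted reassurance; the documents do not show that the primary result would be materially wrong.

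**What to change.** The complete-case primary analysis can stay. In V.1, change the weighting as follows.

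1. Give known deaths by day 60 no walking-response weight. Weight responding survivors by the inverse of the walking-response rate among day-60 survivors in the same arm and stratum. Each cell risk is then P(dead) + P(alive) x P(not walking | alive, responded).
2. For this calculation, count US patients who were searched in the Death Index with sufficient identifiers and had no match as alive at day 60. Handle the remaining patients of unknown vital status in a separate vital-status step with its assumption stated.
3. Repeat the estimate over a range of non-walking rates for non-responding survivors, allowing the rate to differ by arm, because step 1 still assumes that response is random among survivors within a cell.
4. State in VI.1 and VII.4.a how Death Index non-matches are coded.

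The cost is SAP wording and a changed weight in an analysis already planned, with no new data. The small downside is reliance on the completeness of the Death Index when a non-match is taken as alive.
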